- Exposure levels to Second Hand Smoke (SHS) in smoking areas provided by Bars Casinos and Bingo halls etc.

Study Design

Population:

The study population will consist of 30 Asthmatic and 30 Chronic Obstructive Pulmonary Disease (COPD) subjects to be recruited through the European Lung Foundation (ELF) in Hungary Spain and Ireland. (20 subjects in each country)

Inclusion criteria for each patient group:

Confirmed [name] COPD patients

- Current or ex-smokers.
- Fully ambulatory.
- Frequent smoking areas*
- Between 50yrs and 70yrs

Confirmed [name] patients

- Fully ambulatory
- Frequent smoking areas
- Over 18yrs

*Irish law has defined an outdoor smoking area as: A place or premises, or part of a place or premises that, is wholly uncovered by any roof, fixed or mobile. An out door place or premises that is covered by a roof, so long as not more than 50% of the perimeter (outside) is covered by a wall, windows, gate or similar.

Exclusion criteria:

- Under 18yrs
- On Oxygen therapy
- Never smokers in COPD patient group
- Undergoing treatment for acute exacerbations.
- Pregnant women

Primary Endpoints:

- To monitor personal exposure to SHS in areas exempted from legislation in pubs, bars and casinos etc. using novel monitoring technologies.
- To simultaneously monitor the respiratory effects as indicated by changes in respiratory rate and flow and activity levels.

Secondary Endpoints

- Any increase in medication usage
- Unscheduled Primary Care /Hospital visits
- Breath Carbon Monoxide (CO) monitoring pre and post study
- Spirometry pre and post exposure

Ethics:

Ethical approval will be sought from DIT Ethics Committee prior to beginning of the project. All documentation relating to the project will be provided for ethical review. There are no perceived Ethical issues as patients will be fully informed and there will be no intervention other than monitoring. It was considered that requesting subjects to go into outside smoking areas might be a problem so only subjects who already frequent such areas will be recruited.

All participants will be provided with a patient information leaflet and asked to sign an informed consent form. (Appendix 1)

Methodology:

Recruitment

Relevant patient organisations will be identified in each country through European Lung Foundation (ELF) ([name]) and project partners.

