Each patient will visit the centre on 2 occasions the first at enrolment and training in use of equipment, this should be at least 2 to 4 hours prior to exposure. The second will be at least 24hrs post exposure to secondhand smoke at, at least one outing to an outdoor smoking area. The duration of time to be spent in the outdoor smoking area is to be a minimum of 15 mins with a preferable time of 30-60 mins.

Spirometry and Breath Co are to be done for at least 2 to 4 hours prior to exposure and 24 hrs post exposure, at the second visit to the research centre.. At the follow up visit all data will be downloaded and checked and any anomalies will be addressed and clarified with the patient.

National Partners will be trained in the use of devices measuring exposure using AirSpeck and respiratory rate using RESpeck. Data will be transmitted to server at the Centre for Speckled Computing via Internet or mobile phone technology where the data will be analysed.

Subsequently patients in each of 3 countries will be shown how to wear and carry the personal monitor devices , ensuring data is recorded.

Data collection, analysis and report writing: This will be carried out by TFRI in collaboration with Project Partners and in consultation with [name].

Table of tasks

	Baseline visit Minimum of 2 to 4 hrs pre exposure	Post exposure visit Minimum 24hrs post exposure
Consent and information sheet	✓	
Recruitment Questionnaire	✓	
CAT/ACT form	✓	
CO Reading	✓	✓
Spirometry	✓	✓
Training of fitting and use of Respiratory device	✓	
Training and fitting of Particle monitor	✓	
Retrieve equipment and check data recorded		✓
Check patient entries and resolve any data queries		✓
Download data and send to TFRI		✓
Check devices working correctly for next subject		✓

Other support for the Project:

[name]

ELF

Asthma society Ireland

Advisory Panel: Tack Project Partners:

[name]

[name]

[name]

[name] [name]

[name] [name]

[name]

Safety Considerations

The safety of all research participants will be considered at all times, they will be seen in an insured medical practice. All personnel dealing with patients will be fully trained and insured.

The Project will be registered at www.clinicaltrials.com

Data Management and Statistical Analysis:

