All data will be stored on a secure server and will be de-identified. Data will be entered giving each participant a unique identifier code; neither their name, address nor date of birth will be recorded in order to protect the confidentiality of the participant. Analysis will be carried out on a blinded dataset using SPSS. Data will be presented as mean and standard deviation (\pm SD) for continuous variables, or percentage for qualitative variables, as appropriate, or their 95% confidence interval. Differences within groups will be compared with Chi² tests for categorical

variables and Student t test for continuous variables. A p value lower than 0.05 will be considered statistically significant.

Quality Assurance:

Baseline and post exposure data re CO readings, Peak flows any change in medication usage or unscheduled hospital or Dr visits will be entered at source and will be verified by the clinical nurse specialist. Patients will be asked to keep a record of any increase medication usage as well as document any Doctor or Hospital visits as well as description of outdoor smoking area visited. (Appendix 6)

All digitally recorded data will be downloaded from the device to a secure server. A Post Doc and or a Research assistant working with TFRI with advice from partners will further examine study data. Any anomalies found will be addressed and resolved from source data.

Expected Outcomes of the Study

- Exposure levels in the home
- Exposure levels in Smoking areas
- Respiratory symptoms pre and post exposure

Dissemination of Results and Publication Policy:

It is intended that research findings will be published in the form of peer reviewed research articles in first-line high impact or open access journals, and also the presentation of the main results in international tobacco control conferences, such as the European Tobacco or Health Conference, or the Annual or the European Meetings of the Society for Research in Nicotine and Tobacco. There will be a final TackSHS conference in which the main findings will be presented to patients, stakeholders, and policy makers. Together with this, dissemination materials (i.e., factsheets, press releases) will be produced and published in

the TackSHS website as well as disseminated through the websites of the collaborating partners and stakeholders. The results will also be EU deliverables for TackSHS project.

Problems Anticipated:

Recruitment

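### The medication endpoint counts only increases, with no reference period or control, so chance increases cannot be told apart from an effect of second-hand smoke

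*Combined protocol and SAP*

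**What the plan says.** Three places in the protocol bear on this endpoint, and they do not agree on direction.

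- Secondary Endpoints: "Any increase in medication usage". No drug class, threshold, reference period or comparator is attached.
- Quality Assurance, on what the patient does: "Patients will be asked to keep a record of any increase medication usage".
- Quality Assurance, one sentence earlier, on what staff enter: "any change in medication usage or unscheduled hospital or Dr visits will be entered at source". This wording is not limited to increases.
- Appendix 6, the subject data collection form: a medication field with a quantity beside it. The form as available shows no separate column for use before the outing or for usual use.

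The design is one exposed cohort: "The study population will consist of 30 Asthmatic and 30 Chronic Obstructive Pulmonary Disease (COPD) subjects". There is no unexposed period or group. Under Patient Schedule the first visit has only a short minimum lead time ("this should be at least 2 to 4 hours prior to exposure"), and the second is a day or more after exposure with no upper limit.

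The statistical section is generic. It says "Differences within groups will be compared with Chi² tests for categorical" variables and Student's t test for continuous ones, and "A p value lower than 0.05 will be considered statistically significant". Nothing in it is specific to medication use. The only question on how often reliever medication is used is item 4 of the Asthma Control Test in Appendix 7. It goes to asthma patients at the baseline visit and asks about the past four weeks. The COPD Assessment Test has no medication item.

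**The concern.** If SHS does nothing, medication use still goes up in some patients and down in others. A rule that counts the first group and ignores the second has an expected count above zero under no effect, unless no patient's use varies at all. The bias lies in the rule, so adding a pre-exposure value while still counting only increases would not remove it. With no control period, the study also has no way to show what count chance alone would give.

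What is at stake is the reading of one secondary endpoint. A count of patients with increased use, out of 30 asthma or 30 COPD patients, has no yardstick. The primary endpoints are not affected.

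**Working it through.** The plan gives no event rate, variance, effect size or sample-size calculation for this endpoint, so there is no figure to reproduce. The check asks how many increases would be expected with no effect.

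**Inputs from the documents.** 30 asthma and 30 COPD patients, significance level 0.05, no control condition.

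**Assumptions (not in the documents).** As-needed use is counted over two equal 24-hour periods, before and after the outing. The two counts are independent with the same mean m. The values of m are chosen to span the answer categories of Asthma Control Test item 4, which run from no use to three or more times a day.

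**Formula.** With identical distributions before and after, increases and decreases are equally likely, so P(increase) = (1 − P(no change))/2. For Poisson counts, P(no change) = exp(−2m)·I0(2m), where I0 is the modified Bessel function of order zero.

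| Assumed use | m per 24 h | P(no change) | P(increase) | Expected increases per 30 |
|---|---|---|---|---|
| None | 0 | 1.000 | 0% | 0 |
| 1 per week | 0.143 | 0.767 | 11.7% | 3.5 |
| 2.5 per week | 0.357 | 0.554 | 22.3% | 6.7 |
| 1 per day | 1 | 0.309 | 34.6% | 10.4 |
| 1.5 per day | 1.5 | 0.243 | 37.8% | 11.4 |
| 3 per day | 3 | 0.167 | 41.7% | 12.5 |

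**Sensitivity to the distribution.** Negative binomial counts (dispersion parameter 1) give 11% at one use per week and 43% at three per day. Underdispersed binomial counts give 34% at 1.5 per day and 39% at three per day. Seven-day windows with Poisson counts give 35% to 47% over 1 per week to 3 per day.

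**Sensitivity to the patient mix.**
- Equal fifths at m = 0, 0.143, 0.357, 1.5 and 3: (0 + 11.7 + 22.3 + 37.8 + 41.7)/5 = 22.7%, or 6.8 of 30.
- A mostly well-controlled mix of 40/30/15/10/5% over the same five rates: 0.30 × 11.7 + 0.15 × 22.3 + 0.10 × 37.8 + 0.05 × 41.7 = 12.7%, or 3.8 of 30.
- Without a distribution, the chance share of increases is half the share of patients whose use changes at all. If only 5% to 10% change, it is 2.5% to 5%, or 0.75 to 1.5 of 30.

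**Unequal windows.** If raw counts over 4 hours before were set against 24 hours after, P(increase) with no effect would be 13% at one use per week and 87% at three per day. The plan does not say this will be done. It shows why the two periods should be of equal length.

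**Counting both directions.** Under the same model, increases and decreases balance: about 3.5 up and 3.5 down of 30 at one use per week, and about 12.5 and 12.5 at three per day. In 20,000 simulated studies per setting, a two-sided exact sign test of increases against decreases rejected in 1.6% to 3.8% of studies (30 or 60 patients, 1 per week to 3 per day), below the stated 0.05.

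**The case against.** The strongest reply is that the calculation models a procedure the protocol does not contain. No dose-by-dose count over matched periods is planned. Patients note an increase on their own judgement, presumably against their usual use, and may not report one extra dose. Medication use may also include fixed regimens that hardly vary. This stands: the percentages are not this endpoint's false-positive rate.

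A reader might infer that a sizeable share of patients will be recorded as showing an SHS effect. The documents do not support that. They give no use rates, the range starts near 0%, and no test or attribution rule is tied to this endpoint. Nor do they support the inference that the endpoint can never show no effect: few or no increases is a possible result, especially where as-needed use is low.

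A reader might also infer that decreases are never captured. The source-entry sentence refers to any change and Appendix 6 records a quantity, so some decreases may be recoverable. The form's layout may have been damaged when the text was read, and the patient information sheet was not available for this review, so fuller diary instructions cannot be ruled out. What remains is that the endpoint and the stated patient instruction name one direction while two other places do not.

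Finally, the missing comparator is arguably the larger gap, since against a matched unexposed period even a count of increases could be interpreted. That is fair, and counting both directions does not supply a control. It does remove the one-sided bias, which is a separate fault.

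**Conclusion.** The point holds as a fault in the endpoint rule and an inconsistency in the text. The endpoint and the patient instruction count increases only, with no reference period or control, so chance increases cannot be separated from an SHS effect. The wording on direction must be reconciled across Secondary Endpoints, Quality Assurance and Appendix 6.

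The size is unknown. Under equal 24-hour windows, independent Poisson counts and no effect, the share counted as increased is about 0% with no as-needed use, about 12% at one use per week and about 42% at three per day. These figures illustrate the mechanism and do not predict this cohort. If few patients use as-needed medication, the problem is small in number, though the rule remains one-sided.

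**What to change.** Reword the endpoint as change in medication use, and align both Quality Assurance sentences and Appendix 6 with it. Record all as-needed use, up or down, over a reference period before the outing and a period of the same length after it. Because Patient Schedule allows the baseline visit only a few hours before exposure, the earlier period needs either recall taken at that visit or a short diary begun beforehand. Report the numbers increased, unchanged and decreased in each disease group, and test the within-patient difference with a sign test or Wilcoxon signed-rank test. Make the change before data collection, because decreases that are never recorded cannot be recovered.

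The cost is wording in two sections, a slightly longer form and some recall error in the pre-exposure period. A diary started before the baseline visit would also need a small change to the schedule. The comparison stays uncontrolled: a net change still could not be attributed to SHS rather than to other aspects of the outing, and the report should say so.

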Appendix 2:

Recruitment Questionnaire

Tackling secondhand tobacco smoke and e-cigarette emissions: **exposure assessment**, novel interventions, impact on lung diseases and economic burden in diverse European populations. The TackSHS Project.

New approaches to monitoring exposure to air pollution and health effects

Researcher: [name]

This is a short questionnaire to ascertain personal smoking status, other sources of exposure, average weekly exposure in hospitality premises, and experience of respiratory symptoms. Please circle your response where appropriate.

Unique Identifier code: XXXX

1. Are you Male Female
2. What is your age?
3. Do you ever smoke cigarettes/tobacco? Yes/No

If yes

- for how many years?
- At what age did you start to smoke?
- Do you smoke everyday Yes/No
- How many do you smoke on an average per day?

4. Do you currently live with any smokers? Yes/No

4. Do you currently live with any smokers? Yes/No

If yes

- how many?
- do they smoke in the home?

5. Are you exposed to smoking in cars? Yes/No

If yes

- How many trips per week?
- What is the average duration of these trips?

6. Do you visit smoking areas in the hospitality sector such as Pubs or Restaurants?

Yes/No

If yes:

- How often per month?

Neither

If yes how long is it since your diagnosis? -----Years -----Months

8. Do you suffer from any of the following?

Wheeze	Never	Sometimes	Often
Cough	Never	Sometimes	Often

Shortness of breath	Never	Sometimes	Often
Stinging or irritation of the eyes	Never	Sometimes	Often

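### No exposure-free interval is set before baseline and time since last smoke exposure is not recorded, so the secondary pre/post change in spirometry and breath CO may be biased by an unknown amount, probably towards zero.

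*Combined protocol and SAP*

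**What the plan says.** - **Who is enrolled.** Both disease groups carry the inclusion criterion "Frequent smoking areas", with no number attached, and the Ethics section repeats the restriction: "so only subjects who already frequent such areas will be recruited". The COPD group admits "Current or ex-smokers". The asthma group has no smoking-status criterion.
- **When baseline is taken.** On the first visit, the Patient Schedule says "this should be at least 2 to 4 hours prior to exposure". On the follow-up visit it says "The second will be at least 24hrs post exposure to secondhand smoke", with no upper limit. The measurements tied to the two visits are lung function and CO: "Spirometry and Breath Co are to be done for at least 2 to 4 hours prior to exposure and 24 hrs post exposure". Both are listed under Secondary Endpoints.
- **What is asked about other exposure.** Appendix 2 asks about the patient's own smoking, monthly visits to smoking areas, the home ("Do you currently live with any smokers? Yes/No") and cars ("Are you exposed to smoking in cars? Yes/No"). In the text available it does not ask when the last exposure or last cigarette was. Appendix 6 logs the study outing, with no field for exposure before baseline.
- **What is done with it.** Data Management and Statistical Analysis specifies within-group t tests and chi-squared tests. It gives these answers no role.
- **What is built differently.** The RESpeck section summarises respiratory rate before, during and after the outing itself, not across the two visits.

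**The concern.** A within-patient change is only as good as its reference value. Here the reference is called pre-exposure, but the only timing rule looks forward to the next outing. A habitual visitor could be measured the morning after a previous outing, or shortly after smoking a cigarette, and the record would not show it.

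The plan itself expects effects to last. It measures 24 hours or more after exposure and lists symptom lag under Problems Anticipated. An effect worth looking for that long after the study outing could equally be present that long after the previous one. With no control group and no smoke-free comparison day, nothing else in the design would reveal this. A flat spirometry result could then be reported as absence of harm when the two values were simply taken in similar states. Time since last exposure cannot be reliably reconstructed afterwards.

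**Working it through.** **Plan's own figures.** 30 asthma + 30 COPD = 60 and 3 countries × 20 = 60, so the sample size is internally consistent. No effect size, SD or power is stated, so nothing further can be reproduced.

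**Inputs.** The 24-hour minimum to the second visit comes from the Patient Schedule and n = 30 per disease group from Population. Visit frequency v per month is assumed, because the plan does not define frequent. A two-sided paired t test at 0.05 is assumed; the plan gives the 0.05 level but neither pairing nor sidedness.

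**Step 1: share of baselines close to an earlier visit.** With visits at random times, the share within 24 hours is f = 1 − exp(−v/30).

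| v per month | f | expected of 60 |
|---|---|---|
| 1 | 1 − exp(−1/30) = 3.3% | 2 |
| 4 | 1 − exp(−4/30) = 12.5% | 7.5 |
| 12 | 1 − exp(−12/30) = 33% | 20 |

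Because 24 hours is a minimum, longer gaps also count as post-exposure. At v = 4, 1 − exp(−8/30) = 23% fall within 48 hours and 1 − exp(−12/30) = 33% within 72 hours. Home, car and own smoking would add to these shares by an amount the documents do not give.

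**Step 2: bias if recent exposure puts the patient in one saturated state.** The post value is always exposed and a fraction f of pre values is too, so the expected change is (1 − f) × true effect. Take a standardised change of 0.53, which n = 30 detects with 80% power:

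- v = 4: 0.53 × 0.875 = 0.46, power 69%.
- v = 12: 0.53 × 0.67 = 0.36, power 47%.

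**Step 3: bias if effects add up and decay.** Let the half-life be h hours, with baseline at 0, the outing at 4 and the second visit at 28 hours. The true effect at the second visit is 0.5^(24/h).

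- *Background visits continue at the same rate after baseline.* Their expected contribution is equal at both visits and cancels, so the retained ratio is 1.
- *The study outing is the only exposure after baseline.* The expected residue at baseline is R = (v/720) × h/ln 2, of which R × 0.5^(28/h) remains at 28 hours. The retained ratio is 1 − R × (1 − 0.5^(28/h)) / 0.5^(24/h).
  - v = 4, h = 6: R = 0.048; 1 − 0.048 × 0.961/0.0625 = 0.26.
  - v = 4, h = 48: R = 0.385; 1 − 0.385 × 0.333/0.707 = 0.82.
  - v = 8, h = 6: R = 0.096; 1 − 0.096 × 0.961/0.0625 = −0.48.
  - v = 8, h = 48: R = 0.769; 1 − 0.769 × 0.333/0.707 = 0.64.

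A simulation of this case gave 0.27, 0.82, −0.47 and 0.63.

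**Step 4: would a 24-hour gap before baseline be enough?** One earlier exposure g hours before baseline contributes 0.5^(g/h) there; the study outing contributes 0.5^(24/h) at a second visit 24 hours later. At g = 24 the two are equal, whatever h is. The baseline gap must exceed the post-exposure gap to help.

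**The case against.** The strongest reply is that a stable background cancels. Patients who visit smoking areas regularly will go on doing so, the same background sits in both measurements, and the change still isolates the extra outing. Step 3 confirms this when effects are additive and exposure is equally likely before and after baseline. But the study is purely observational, so the study outing may simply be the patient's usual visit rather than an extra one, and nothing recorded shows which applies.

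Three stronger readings are tempting, and the documents do not support them.

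- *Many baselines are contaminated.* Frequent is undefined, and at one visit a month the share from venue visits is only about 3%.
- *The effect certainly shrinks.* That depends on the model: it can shrink, cancel or change sign, and heavier exposure after baseline than before would inflate it.
- *The trial's main result is compromised.* The visit pair serves secondary endpoints, while respiratory rate is compared around the outing.

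Two further points stand. AIRSpeck is fitted at baseline, so exposure between fitting and outing can be seen, though not exposure before fitting. And Appendix 1 and part of Appendix 2 are not visible in the text reviewed, so an instruction to participants or a lost question there cannot be excluded.

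**Conclusion.** The gap is real and worth closing before data collection. In the text available, nothing secures or documents the unexposed state of the baseline spirometry and CO values, in a population chosen for regular exposure and partly eligible as active smokers. The resulting bias is probably towards zero: the saturated-state model and the case with no further exposure after baseline both weaken the contrast, while a stable additive background leaves it unchanged. Its size cannot be stated. Across 1 to 12 assumed visits a month, 3% to 33% of baselines fall within 24 hours of an earlier venue visit, before home, car or own smoking is counted. These shares assume random visit times, and the effect on the contrast also depends on an unknown decay.

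The primary respiratory-rate comparison is touched only if earlier exposure carries into its before-outing recording.

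**What to change.** - At both visits, record the date and time of the last smoking-area, home and car exposure, and of the last own cigarette. Add a line to Appendix 6 for other secondhand smoke between the visits.
- Where possible, schedule baseline as long as practicable after the last outing, and longer than the gap from the study outing to the second visit. A gap of only 24 hours would not clear an effect that the plan looks for at 24 hours or later.
- Keep all patients in the main analysis; restricting groups of 30 to those with a clear baseline would cost precision and select the least exposed. Prespecify a sensitivity analysis of spirometry and CO change by time since last exposure and by own smoking. Use the AIRSpeck trace to describe exposure between baseline and outing.
- State in the analysis plan that a null spirometry result cannot be read as no effect if baselines were recently exposed.

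The cost is a few form lines, some moved appointments and a sensitivity analysis whose subgroup results will be imprecise.

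### Breath CO is read at least 24 h after the outing, and no available form records the patient's own cigarettes between visits, so a pre/post difference cannot be attributed to the outing

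*Combined protocol and SAP*

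**What the plan says.** All references are to the combined protocol and SAP.

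- **Status of CO.** Secondary Endpoints lists "Breath Carbon Monoxide (CO) monitoring pre and post study". Quality Assurance also groups CO with the baseline and post-exposure data. What the endpoint is meant to show is not explained.
- **Timing.** Patient Schedule states: "Spirometry and Breath Co are to be done for at least 2 to 4 hours prior to exposure and 24 hrs post exposure". It also says of the visits: "The second will be at least 24hrs post exposure to secondhand smoke at, at least one outing to an outdoor smoking area". The Table of tasks ticks CO once at each of the two visits and heads the second column "Minimum 24hrs post exposure". Taken together, there is one reading before the outing and one at the second visit, with a floor of 24 h and no ceiling.
- **Who may enter.** The COPD criteria admit "Current or ex-smokers". The asthma criteria do not mention smoking.
- **Own smoking.** The recruitment questionnaire in Appendix 2 asks about habit: "How many do you smoke on an average per day". It also asks about household smokers and smoking in cars. Appendix 6, completed around the outing, counts other smokers and e-cigarette users present and has lines for exposure times, unusual events and medication. It has no line for the patient's own cigarettes.
- **Analysis.** Data Management and Statistical Analysis compares differences within groups by Chi² tests for categorical "variables and Student t test for continuous variables", at p below 0.05. There is no analysis specific to CO.

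**The concern.** A secondary endpoint measured before and after an exposure will normally be read as an effect of that exposure. Here three things stand between the outing and the second reading: a delay of unlimited length, whatever the patient smoked in that time, and any other exposure at home, in cars or at a further outing. The device responds to active smoking; Appendix 3 presents one of its two models as a screen for cigarette consumption.

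Two wrong conclusions could follow. A change in CO could be reported as uptake of secondhand smoke when it reflects a cigarette smoked shortly before one of the visits. An absence of change could be reported as no uptake when any rise had already washed out. Cigarettes that are not recorded at the time cannot be recovered reliably afterwards.

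**Working it through.** The plan gives no power, effect size or standard deviation (SD) for CO, so there is no figure to reproduce. The sample size agrees with itself: 30 + 30 = 60 patients, and 3 countries × 20 = 60.

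**Step 1. Attribution (no outside figure needed).** The pre/post difference in one patient is the sum of:

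(a) what is left of any rise from the outing or outings;
(b) the difference in own smoking before the two readings;
(c) the difference in other exposure before the two readings;
(d) measurement error.

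To isolate (a), the plan would need to measure (b) and (c) or have an unexposed period in which they also operate. For (b), the available forms give only a habitual daily number at recruitment. For (c), they give habitual household and car exposure at recruitment, together with particulate data from AirSpeck; "Exposure levels in the home" is an expected outcome. No unexposed period is described. Term (a) is therefore not identified. In non-smokers (b) is absent, but (c) and the delay remain.

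**Step 2. How much of a rise is left (illustration).** Assume first-order washout: fraction left = 0.5^(T/h), with T the hours since the outing and h the half-life. The documents give no half-life; 2 to 8 h is assumed.

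| h | Left at T = 24 h | Left from an assumed 5 ppm rise |
|---|---|---|
| 2 h | 0.5^12 = 0.02% | 0.001 ppm |
| 4 h | 0.5^6 = 1.6% | 0.08 ppm |
| 6 h | 0.5^4 = 6.25% | 0.31 ppm |
| 8 h | 0.5^3 = 12.5% | 0.63 ppm |

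At 48 h, which the plan permits, the most favourable case leaves 0.5^6 = 1.6%. Appendix 3 gives a resolution of 1 ppm for one of the two monitors.

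**Step 3. What a test could detect (illustration).** For a two-sided paired t test at 0.05 with 80% power, the smallest detectable mean change is 0.53 SD of the differences for n = 30 (one disease group) and 0.37 SD for n = 60. With an assumed SD of 1 ppm, these are 0.53 and 0.37 ppm. Over an assumed grid of half-lives of 2, 4, 6 and 8 h, rises of 2 and 5 ppm, and SDs of 1, 2 and 3 ppm, power at 24 h reaches 80% in only one combination: 8 h, 5 ppm, SD 1 ppm (91% at n = 30, 99.7% at n = 60). At 48 h the highest power anywhere on the grid is 7% (n = 30) or 9% (n = 60).

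**Step 4. Size of the competing term (illustration).** If a share f of a group smokes and the timing of their own cigarettes moves their mean reading by c ppm between visits, the group mean moves by f × c. With assumed f = 0.25 to 0.75 and c = 2 to 5 ppm, this runs from 0.25 × 2 = 0.5 ppm to 0.75 × 5 = 3.75 ppm. Even the smallest value exceeds every residual in Step 2 except the 0.63 ppm case. If the timing varies at random instead, the mean does not shift, but the SD grows and power falls further.

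**The case against.** The strongest reply is that CO is one of four secondary endpoints in a monitoring study without an intervention. Exposure, a primary endpoint, is measured by AirSpeck; CO does not appear under Expected Outcomes; and no claim based on CO is announced. That stands, and it limits the weight of this point.

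Second, CO might be only a check of smoking status, in which case the delay hardly matters. The plan does not say this. The idea rests on product literature in Appendix 3, whereas Secondary Endpoints, the Table of tasks and Quality Assurance all treat CO as a before/after measure. If a smoking check is intended, the plan should say so.

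Third, a t test is not certain. Devices used to gather data describes the monitor by colour bands, and Appendix 3 describes one model that reports ranges. CO could be analysed in categories by Chi². This stands, and Step 3 then does not apply. Step 1 is unchanged.

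Fourth, a reader might infer that own smoking goes wholly unrecorded. The documents do not support that. Habitual smoking is asked at recruitment, the unusual-events line could catch some cigarettes, anomalies are clarified with the patient at the second visit, and some pages are not in the available text (those before Appendix 2 and part of Appendix 3). The supportable statement is that no available form has a field for it. For a daily smoker, a cigarette is neither unusual nor an anomaly.

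Fifth, the half-lives, rises and SDs are all assumed, and a count of grid combinations is not a probability. This stands; Steps 2 to 4 only illustrate scale.

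**Conclusion.** The point holds in a limited form. With the present schedule and forms, a pre/post CO difference cannot be attributed to the outing. This rests on the documents alone: one late reading with no upper limit, more than one outing allowed, current smokers eligible, no field for own cigarettes in the available forms, and no unexposed comparison.

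That a null is likely to be uninformative is a weaker statement. It depends on the assumed half-life of 2 to 8 h, under which 0.02% to 12.5% of a rise remains at 24 h, and on assumed rises and SDs.

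Three stronger readings might be inferred and are not supported:

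- **That the plan gives CO no role.** It is a named secondary endpoint; only its purpose is unexplained.
- **That a null could never be informative.** With a slow half-life, a large rise and a small SD, power at exactly 24 h is high.
- **That the study's main results are compromised.** The primary endpoints do not use CO.

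This is a cheap improvement to one secondary endpoint, best made before data collection.

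**What to change.** 1. Add a line to Appendix 6 for the patient's own cigarettes between visits, and record the time of the last cigarette before each CO reading.
2. Report CO change separately for current smokers and non-smokers.
3. Record the actual time of the second reading and report with the CO result the interval from the last outing. Appendix 6 already has the end of exposure and the next appointment, so only the actual reading time, and which outing was the last, need adding.
4. With the existing schedule, state that neither a difference nor a null at 24 h or later is interpreted as CO uptake from the outing. Say what the endpoint is for, and word Secondary Endpoints, Patient Schedule, and Data Management and Statistical Analysis consistently. The purpose is the sponsor's choice; verifying smoking status is one that the existing readings can serve.

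If the sponsor does want CO to measure uptake, a reading soon after the outing would be needed. That changes the schedule, is not part of this low-cost fix, and would still need item 1.

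**Cost.** One more diary item, a few clock times and wording in three sections; no extra visit or device. The subgroups in item 2 are smaller than 30 per disease group wherever a group mixes smokers and non-smokers, so CO is estimated less precisely. One secondary endpoint carries a narrower interpretation.
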